2.3.2 Secondary Endpoints

The secondary outcomes are measures of the efficacy of the ATIMP; these will be performed on an individual participant basis and will be descriptive in nature:

- 1) Any improvements in visual function from baseline that are greater than the test-retest variation and are sustained for at least two consecutive assessments.
- 2) Any improvement in retinal function from baseline that is greater than test-retest variation and measurable by electrophysiology (pattern ERG, or full-field ERG).
- Quality of life will be measured by the Impact of Visual Impairment (IVI) questionnaire and the EQ5D-5L.

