#### 5.9.3 Statistical Methods

A formal Statistical Analysis Plan (SAP) will be written by the Sponsor for each gene defect programme. Analysis of the primary and secondary outcomes will be descriptive in nature. All outcomes for each product will be analysed and reported separately.

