#### 5.9.3.2 Statistical Methods - Secondary Outcome Analysis

The secondary outcomes are measures of the efficacy of each ATIMP; these will be performed on an individual participant basis and will be primarily descriptive in nature. Standard assessments will be used to measure visual function and established methods of analysis, appropriate for the assessment will be used to evaluate the data. For specialist assessments, data will be analysed by the expert team member(s) who developed the assessment. Final data will be reported descriptively.

Efficacy will be indicated by:

- 1) Any improvement in visual function from baseline that is greater that the test-retest variation for that test and is sustained for at least 2 consecutive assessments.
- 2) Any improvement in retinal function from baseline that is greater than test-retest variation and measurable by electrophysiology (pattern ERG, or full-field ERG).

Measures will be reported individually and aggregated across participants as the proportion who satisfy the above criteria.

Quality of life patient reported outcome measures will be used to correlate a participant's feeling about their own wellbeing with clinical observations.

Any deviations from the original statistical plan will be described in the final report, as appropriate.

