1 INTRODUCTION

The purpose of this Statistical Analysis Plan (SAP) is to provide a description of the statistical methods to be implemented for the analysis of data from the study with protocol number MGT007. The SAP will be finalized prior to database lock. Any deviations from the SAP after database lock will be documented in the final Clinical Study Report (CSR).

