2.1.2 Secondary Objective

The secondary research objective is to explore the longer-term efficacy of AAV8-hCARp.hCNGB3 and AAV8-hG1.7p.coCNGA3 in improving visual and retinal function, and quality of life.

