3.2.2 Full Analysis Set (FAS)

The Full Analysis Set (FAS) includes all enrolled participants who were diagnosed with CNGA3- or CNGB3-related achromatopsia, who were administered vector, and who had at least one post-baseline assessment for efficacy. Participants will be presented according to the dose level they received.

Study completion/withdrawal and protocol deviations will be summarized using the FAS set. Background and demographic characteristics will be summarized using the SAF. The primary and secondary efficacy endpoints will be summarized using the FAS. Prior/concomitant medications, administration of study treatment, and exposure and safety will be summarized using the SAF.

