3.5 Efficacy Evaluation

3.5.1 Test-Retest

The test-retest values from studies MGT006 and MGT012 will be used for the MGT007 final analyses.

The protocol describes efficacy as being indicated by:

Any improvement in visual function from baseline that is greater than the test-retest variation for that test and is sustained for at least 2 consecutive assessments.

Participants who have a post baseline reading greater than the test-retest value for at least 2 consecutive assessments will be classed as a visual function improvement for the relevant test.

The test-retest variation for each visual function assessment will be calculated for each participant who has at least one set of test-retest data as:

$$Test - retest = 1.96 \sqrt{S_p^2}$$

where S_p^2 is the within-participant variance for each participant and will be derived as:

$$\frac{(n1-1)\sum_{(yi1-ybar1)}2+(n2-1)\sum_{(yi2-ybar2)}2}{n1+n2-g}$$

Where:

yi1 is the ith baseline observation in the left eye
ybar1 is the mean of baseline observations in the left eye
yi2 is the ith baseline observation in the right eye
ybar2 is the mean of baseline observations in the right eye
n1= number of baseline observations in the left eye
n2= number of baseline observations in the right eye
g is the number of eyes =2

The test-retest variation for each visual function assessment of the difference between the study eye and fellow eye will also be calculated for each participant who has at least one set of test-retest data using the same formula except S_n^2 will be derived as

$$\frac{\sum_{(yi-ybar)}2}{n-g}$$

Where:

yi is the ith baseline observation in the difference of the study eye and fellow eye ybar is the mean of baseline observations in the difference of the study eye and fellow eye n= number of baseline observations in the difference of the study eye and fellow eye (vary from 2 to 3) g is 1

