4 CHANGES FROM PROTOCOL-SPECIFIED ANALYSIS

- Samples for immunological response will be stored and will not be analyzed at this time.
- Videos of photoaversion test will be stored for future use and will not be analyzed at this time.
- Data from the following assessments will not be analyzed:
 - o computerised (achromatic) spatial contrast sensitivity function tests
 - Colour Vision
 - Octopus Perimetry
 - Optical Coherence Tomography
 - Photoaversion
 - o Full field electroretinography
 - Pattern electroretinography
 - o Adaptive optics imaging
 - o Full Field Stimulus Testing

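### The ERG retinal-function endpoint stays in the SAP, but both ERG tests are excluded from analysis with no reason given and the endpoint is not withdrawn

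*SAP*

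**What the plan says.** The SAP keeps the endpoint in two places. Section 2.1.2 gives the secondary objective as exploring efficacy in "improving visual and retinal function, and quality of life". Section 2.3.2 lists, as endpoint 2, "Any improvement in retinal function from baseline that is greater than test-retest variation and measurable by electrophysiology (pattern ERG, or full-field ERG". This matches Protocol 5.5.2.

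On analysis, SAP 3.2.2 says "The primary and secondary efficacy endpoints will be summarized using the FAS", with no exception for ERG. Protocol 5.9.3.2 names two efficacy criteria, one for visual function and one for ERG, and adds "Measures will be reported individually and aggregated across participants as the proportion who satisfy the above criteria".

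SAP 4, under its heading on changes from the protocol, states "Data from the following assessments will not be analyzed". The list that follows includes both full-field and pattern electroretinography. No reason is attached, and endpoint 2 is not mentioned.

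The ERG visits come from Protocol 5.6: Months 12, 24, 36, 48 and 60, with testing to stop after Month 12 in a participant whose responses remain undetectable.

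**The concern.** Pattern and full-field ERG are the only measures named for endpoint 2 and the only electrophysiology tests on the schedule. Once both are excluded, the endpoint has no route to a result. The other exclusions in SAP 4 do not have this effect on a named endpoint: dropping colour vision or perimetry still leaves visual acuity, contrast sensitivity and reading speed for endpoint 1.

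What is lost is the retinal-function part of the secondary objective. Protocol 5.4.1.1.2 uses ERG to assess the rod and cone systems and macular function, and Protocol 4.1 presents restored cone function as the outcome of interest in this disease. The efficacy measures that remain (acuity, contrast, reading, questionnaires) all depend on the participant's own responses in an open-label study.

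**Working it through.** The SAP gives no figure to reproduce. The check is a comparison of sections, followed by a count of the data affected.

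**Step 1: follow each secondary endpoint from definition to analysis.**

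| Endpoint in SAP 2.3.2 | Analysis in SAP 3.5 | Status after SAP 4 |
|---|---|---|
| 1. Visual function | 3.5.2 to 3.5.4 (acuity, contrast, reading) | Analysed in part |
| 2. Retinal function by ERG | None | Both named tests excluded |
| 3. Quality of life | 3.5.5 | Analysed |

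Endpoint 2 is the only one of the three with no planned summary.

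**Step 2: check whether the responder rule exists.** SAP 3.5.1 says "The test-retest variation for each visual function assessment will be calculated", and of the two criteria in Protocol 5.9.3.2 it restates only the visual-function one. No test-retest rule for ERG is given. This is the same gap as in step 1, seen from the methods side; it is not a second defect.

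**Step 3: check whether other text supplies the result.**
- SAP 5 provides for listings of all available data. ERG values might appear there, but a listing contains no responder classification and no proportion.
- The Protocol 5.6 stopping rule applies participant by participant and only after Month 12. It leaves the Month 12 data in place, and SAP 4 does not cite it as a reason.
- SAP 4 says that immunology samples and photoaversion videos are stored and not analysed for now. It says nothing comparable about ERG.

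**Step 4: bound the scheduled data, per ERG test.** Inputs are 23 CNGB3 and 11 CNGA3 participants dosed (SAP 2.2.3) and five ERG visits (Protocol 5.6). Assume that all dosed participants enrolled and attended.
- All five visits: 23 × 5 = 115 for CNGB3 and 11 × 5 = 55 for CNGA3; total 115 + 55 = 170.
- Testing stopped after Month 12 in everyone: 23 + 11 = 34.

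The range is 34 to 170 participant-visits per test. Actual numbers are not in the documents. They will be lower with non-enrolment, missed visits, or children unable to do the test reliably (Protocol 5.4.1.1).

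Even the lower end could be informative. Unlike the visual-function criterion, the ERG criterion does not require improvement at two consecutive assessments.

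**The case against.** The strongest reply is that there is little real contradiction. SAP 2.3.2 restates the protocol endpoint in a study overview, and SAP 4 declares the departure from it. SAP 3.5 is consistent with SAP 4, and a programmer would know what to run. The sentence in SAP 3.2.2 assigns analysis sets to outputs and is generically worded: it refers to primary efficacy endpoints although the primary endpoint is safety. On this view, only a cross-reference and a rationale are missing.

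Much of this stands. It also rules out several stronger readings that a reader might infer:

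- *That the omission is hidden, or that not analysed could be mistaken for no effect.* SAP 4 states the exclusion openly, so anyone holding the SAP can tell the two apart.
- *That the exclusion followed from the results.* Nothing in the documents shows this. SAP 1 says the SAP is finalised before database lock, which places the decision before lock. In an open-label study that does not establish that ERG data were unseen, but it is no evidence that they were used.
- *That the clinical study report is barred from mentioning it.* SAP 1 says "Any deviations from the SAP after database lock will be documented in the final Clinical Study Report (CSR". It does not limit the report to those deviations, and Protocol 5.9.3.2 provides for deviations to be described in the final report as appropriate. Neither text asks for a reason.
- *That Protocol 5.9.3 independently requires an ERG analysis.* Its sentence "All outcomes for each product will be analysed and reported separately" is mainly about keeping the two products apart.

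The reply does not explain why an endpoint and part of an objective remain listed when no analysis can address them, or on what grounds the tests were dropped.

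**Conclusion.** The point holds as a declared but unexplained exclusion that leaves one of three secondary endpoints without a result and the retinal-function part of the secondary objective unanswered. If the SAP is followed exactly, no proportion improved on ERG will be reported for either product.

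It should be fixed before database lock, but its weight is moderate. The endpoint is secondary and descriptive, and the primary safety outcome is unaffected. The data at issue are between 34 and 170 scheduled participant-visits per test, on the assumption of full enrolment and attendance, and possibly fewer. These counts show how much scheduled information goes unused; they do not measure bias in any conclusion.

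**What to change.** Preferred: add to SAP 3.5 a descriptive ERG summary by product from the data already collected.
- If repeat baseline ERGs exist, give n/N improved above test-retest variation, and add the ERG criterion and the source of its test-retest value to SAP 3.5.1.
- If they do not, give observed values and change from baseline, or detectable versus undetectable response, labelled as supplementary because it is not the protocol criterion.
- In either case, report the number tested and the number stopped after Month 12 as undetectable.

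The cost is some data cleaning, ERG reading if it is incomplete, and a few tables on at most 34 participants, with no new visits. The documents do not say whether repeat baseline ERGs were taken, so the responder form may not be possible.

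If the sponsor keeps the exclusion: mark endpoint 2 as not analysed in SAP 2.3.2 and 3.2.2. In SAP 4 and the clinical study report, state the reason and whether it was decided before ERG data were seen. Draw no efficacy conclusion on retinal function. This needs text changes only, but that part of the secondary objective stays unanswered.

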3 STATISTICAL METHODOLOGY

3.1 General Considerations

3.1.1 Definition of Baseline

The baseline values of MGT006 and MGT012 final analyses will be used for the MGT007 final analyses.

3.1.2 Incomplete Dates

For calculation purposes, incomplete dates will be completed using the most conservative values. For example, AEs with missing start dates, but with stop dates either overlapping the treatment period or missing, will be counted as treatment-emergent, taking the worst-case approach. When partial dates are present in the data, both a partial start date and/or a partial stop date will be evaluated to determine whether it can be conclusively established that the AE started prior to the administration of ATIMP. If the above cannot be conclusively established based on the partial and/or present dates, then the AE will be considered treatment-emergent. Actual data values as they appear in the original eCRFs will be presented in the listings.

3.1.3 Non-numeric Values Recorded in a Numeric Field

In the case where a variable is recorded as ">x", " \geq x", " \leq x" or " \leq x", then for analysis purposes, a value of x will be taken. Where a range of values is quoted, the midpoint of the range will be taken. For example, if a laboratory safety parameter is reported as being below the limit of quantification or < x, the value of the limit will be used in the calculation of summary statistics. The recorded value will be reported in listings.

3.1.4 Summary Statistics

Categorical data will generally be summarized with counts and percentages of subjects. The denominator used for the percentage calculation will be clearly defined. Continuous data will generally be summarized with descriptive statistics including n (number of non-missing values), mean, median, standard deviation, Q1, Q3, minimum, and maximum.

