	3.5.8	Photoaversion (PA)	Error! Bookmark not defined.
	3.5.9	Quality of Life	16
	3.5.10	Multiplicity	18
4	CHANG	GES FROM PROTOCOL-SPECIFIED ANALYSIS	18
5	Progran	nming Specifications	18
App	endix A:	References	19

LIST OF ABBREVIATIONS

Abbreviation	Definition
AE	Adverse event
AO	Adaptive optics
ATIMP	Advanced therapy investigational medicinal product
BCEA	Bivariate contour ellipse area
BMI	Body mass index
CF	Counting fingers
CI	Confidence interval
CMT	Clinical Management Team
CSF	Contrast Sensitivity Function
CTCAE	Common Terminology Criteria for Adverse Events
DA	Dark adapted
ELISA	Enzyme-linked Immunosorbent Assay
ERG	Electroretinography
ETDRS	Early Treatment Diabetic Retinopathy Study
FAF	Fundus Autofluorescence
FAS	Full Analysis Set
FST	Full-field Stimulus Testing
НМ	Hand motion
IDMC	Independent Data Monitoring Committee
ISCEV	International Society for Clinical Electrophysiology of Vision
IVI	Impact of visual impairment
KG	Kilograms
LP	Light perception
MedDRA	Medical Dictionary for Regulatory Activities
mfERG	Multifocal electroretinography
mL	Millilitre
NLP	No light perception
PCR	Polymerase chain reaction
PERG	Pattern electroretinography

Abbreviation	Definition
PT	Preferred term
RPGR	Retinitis Pigmentosa GTPase Regulator
SAE	Serious adverse event
SAF	Safety analysis set
SAP	Statistical analysis plan
SD	Standard deviation
SD-OCT	Spectral domain optical coherence tomography
SOC	System organ class
SUN	Standardisation of uveitis nomenclature
TEAE	Treatment emergent adverse event
UK	United Kingdom
US	United States
VAS	Visual analogue scale
VG	Vector genome
WHO	World Health Organization

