2.2.3 Sample Size Determination

This is a long-term follow-up study; therefore, there is no formal sample size calculation.

23 and 11 participants were randomized and dosed in the MGT006 and MGT012 studies, respectively. All participants enrolled in the MGT006 and MGT012 studies were invited to participate in this follow-up study.

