3.1.5 Data Presentations

All data will be summarized by dose level. For each study, a separate study-specific total should summarize all dose levels for that study. In addition, an overall column that includes all participants of both studies should also be presented.

The following table summarizes the number of dosed participants and the associated dose levels in studies MGT006 and MGT012.

Dose Level (vg/mL)	Number of MGT006 Participants Dosed	Number of MGT012 Participants Dosed
	3	3
	12	3
	3	NA
	5	5
Study Total	23	11

Unscheduled measurements and repeat measurements not due to technical failure will be listed but not summarized. If a repeat measurement is due to a technical failure, it will be included in the summaries.

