3.5.2 Visual Acuity

Visual acuity was assessed at the Month 9, 12, 18, 24, 36, 48, and 60 visits.

4 meter refraction of the sphere, cylinder, and axis of each eye will be measured. Best-corrected ETDRS visual acuity will be measured.

The arithmetic mean of the multiple observations at baseline will be used as the baseline value.

Achievement of visual improvement above the test-retest variation (yes/no) as measured by a number of ETDRS letters will be summarized for study eye and the difference between eyes (study eye minus fellow eye) for all participants.

The 4-meter refraction (sphere, cylinder, and axis) observed values will be summarized for the study eye for all participants.

Summary statistics of all ETDRS visual acuity observed values and the change from baseline by study eye and the difference between eyes (study eye minus fellow eye) for all participants will be presented.

The difference between the study eye and the fellow eye of ETDRS letters, the difference at each visit, along with its change from baseline data, will be summarized. At each post-baseline visit, the change from baseline in the difference between the study eye and the fellow eye will be tested by a nonparametric Wilcoxon signed rank test as the primary method. The p-value from the t-test and the Shapiro-Wilk Normality test will also be provided.

All visual acuity data will be listed.

In-text displays:

- Average Plot of BCVA (ETDRS Letters) Change from Baseline Over Time
- Individual Plot of BCVA (ETDRS Letters) Change from Baseline Over Time

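### The SAP plans no confidence interval for the primary safety proportions, the test-retest responder proportions or the between-eye changes, although it reports unadjusted p-values for the last of these.

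*SAP*

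**What the plan says.** SAP 3.1.4 sets the general output rule. For categorical results, "Categorical data will generally be summarized with counts and percentages of subjects", with the denominator to be made clear. For the rest, "Continuous data will generally be summarized with descriptive statistics including n (number of non-missing values), mean, median, standard deviation, Q1, Q3, minimum, and maximum". No interval or standard error is named.

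The specific sections do not add one:

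- SAP 3.4.1 (adverse events) gives numbers of events and of participants.
- SAP 3.5.2 to 3.5.4 (visual acuity, contrast sensitivity, reading speed) summarise improvement beyond test-retest variation as yes or no. This matches Protocol 5.9.3.2: "Measures will be reported individually and aggregated across participants as the proportion who satisfy the above criteria".
- The same three sections go further for the continuous measures. The rule, applied separately to every assessment after baseline, is that "the change from baseline in the difference between the study eye and the fellow eye will be tested by a nonparametric Wilcoxon signed rank test". In addition, "The p-value from the t-test and the Shapiro-Wilk Normality test will also be provided". SAP 3.5.6 makes no multiplicity adjustment.

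The phrase "Confidence interval" occurs only in the SAP's list of abbreviations.

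On numbers, SAP 2.2.3 says that "23 and 11 participants were randomized and dosed in the MGT006 and MGT012 studies, respectively". SAP 3.1.5 asks for columns by dose level, a total for each study and an overall column for both. Protocol 5.9.3 calls the analysis of primary and secondary outcomes descriptive.

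**The concern.** The primary endpoint in SAP 2.3.1 comes down to two yes/no outcomes per participant: a drug-related adverse event, and a loss of 15 or more ETDRS letters. The first secondary outcome is also a proportion. In groups this small, a proportion says little unless the reader can see what other rates fit the data. A count of zero can be taken to mean that the event does not occur.

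The between-eye comparisons raise the same problem from the other side. A p-value above 0.05 among 11 participants can be taken to mean no effect, when the data may be compatible with a change of several letters. Three measures at the seven MGT007 visits give 3 × 7 = 21 Wilcoxon p-values for each group tested. None has an interval to show how large an effect is supported or excluded.

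**Working it through.** **Inputs.** Dosed participants by dose level come from the table in SAP 3.1.5: 3, 12, 3 and 5 in MGT006, and 3, 3 and 5 in MGT012. The documents give no confidence level, so 95% two-sided is assumed. They give no SD for the change in between-eye difference, so 4 to 8 letters is assumed.

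**Reproducing the plan's totals.** 3 + 12 + 3 + 5 = 23 and 3 + 3 + 5 = 11, as stated. The overall column is 23 + 11 = 34. These are parent-study counts. The number who entered MGT007 is not given, so they are the largest possible denominators, and the limits below are the narrowest possible.

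**Zero events.** The exact (Clopper-Pearson) upper limit for 0 of n solves (1 − p)^n = 0.025, so p = 1 − 0.025^(1/n).

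| Group | n | Upper 95% limit for 0/n |
|---|---|---|
| Smallest dose groups | 3 | 70.8% |
| Dose groups of 5 | 5 | 52.2% |
| MGT012 total | 11 | 28.5% |
| Largest dose group | 12 | 26.5% |
| MGT006 total | 23 | 14.8% |
| Overall | 34 | 10.3% |

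Seen the other way, if the true event rate were 10%, the chance of seeing at least one affected participant is 1 − 0.9^n: 27% at n=3, 69% at n=11, 91% at n=23 and 97% at n=34. So among 11 participants, a 10% event would be missed altogether in about 31% of cases (100 − 69).

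**Responder proportions (invented counts, for illustration only).** Exact 95% intervals from beta quantiles: 5/23 (22%) gives 7.5% to 43.7%, and 3/11 (27%) gives 6.0% to 61.0%.

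**Between-eye change in acuity.** The half-width of a 95% t interval is t(0.975, n − 1) × SD/√n.

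- n=23: 2.074 × 4/√23 = 1.7 letters; with SD 8, 3.5 letters.
- n=11: 2.228 × 4/√11 = 2.7 letters; with SD 8, 5.4 letters.

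Under these assumed SDs, a non-significant result in the MGT012 total could still be compatible with a mean change of several letters in either direction.

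**The case against.** The strongest defence is that this is a declared descriptive study: no comparator, no hypothesis and no sample-size calculation. Leaving out intervals contradicts nothing in the documents. The information is not lost either. Counts appear with defined denominators, so a reader sees 0 of 3 rather than a bare 0%. The n, mean and SD allow a t interval to be worked out. All data are listed, and individual plots are planned for the three efficacy measures. All of that stands, and it keeps the point modest. It does not remove it: an interval needs no hypothesis, and for the between-eye changes the SAP has already moved from description to testing.

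Three stronger readings are tempting, and the documents do not support them.

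- A reader might infer that SAP 3.1.4 confines every result to descriptive statistics. It does not. The rule is qualified as general, the list for continuous data is open-ended, and 3.5.2 to 3.5.4 add p-values.
- A reader might infer from the abbreviation list that intervals were intended and then dropped. The same list carries RPGR, mfERG, BCEA and PCR, which no analysis section uses either, so the entry may simply be carried over from a template.
- A reader might take 23 as the largest group reported. The overall column can reach 34, where the uncertainty is smallest.

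It is also fair to say that intervals at n=3 add little: 0/3 runs to 70.8% and 1/3 runs from 0.8% to 90.6%.

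**Conclusion.** The omission is real and worth correcting as a cheap improvement in reporting. It is not an error that invalidates the analysis. It matters most at study-total level, where the results are likely to be read as conclusions: a zero count would leave true rates of up to 14.8% (n=23) or 28.5% (n=11) open, and 10.3% even in the overall column.

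The limits assume a 95% two-sided level and that everyone dosed entered MGT007; fewer participants would widen them. The letter half-widths depend wholly on the assumed SD of 4 to 8, and the responder examples are not trial data.

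One part cannot be met by adding intervals alone. SAP 2.3.1 makes a loss of 15 or more letters part of the primary endpoint, but neither 3.4 nor 3.5.2 plans a count of participants with such a loss. That tabulation has to be added first.

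**What to change.** In SAP 3.1.4, add exact Clopper-Pearson 95% intervals at study-total level, separately for each product, and by dose level only where useful. Apply them to the proportion of participants with:

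1. a treatment-related TEAE, as defined in 3.4.1;
2. a serious TEAE;
3. a loss of 15 or more ETDRS letters, with a new table for this count;
4. a response beyond test-retest variation, for each measure in 3.5.2 to 3.5.4, for the study eye and for the between-eye difference.

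In 3.5.2 to 3.5.4, place a Hodges-Lehmann 95% interval beside each Wilcoxon p-value and a t-based 95% interval beside each t-test p-value, so that each interval matches its test. Study-total level suits this too. The smallest exact two-sided signed-rank p-value is 2/2^n, which is 0.25 at n=3 and 0.0625 at n=5, so an exact 95% Hodges-Lehmann interval does not exist in groups of those sizes.

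The cost is some SAP wording, one extra table and a little programming. No new data or visits are needed, and SAP section 1 leaves room for the change before database lock. The drawback is that wide intervals will make a 0% or a non-significant result look less conclusive.
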